6.2.2 Dose modification and dose delay of ribociclib+everolimus

Guidelines for dose, modifications, interruptions and re-initiation of ribociclib+everolimus treatment are described in [Table 11](#). The following are the dose modification levels in [Table 10](#).

Table 10 Dose Modification Levels

Ribociclib	
Dose	Number of tablets & strength
200 mg (qd)*	1 x 200 mg tablet
400 mg (qd)	2 x 200 mg tablet
600 mg (qd)	3 x 200 mg tablet

* One dose de-escalation will be allowed below dose level 0 if needed as a dose modification.

Everolimus	
Dose	Number of tablets & strength
2.5 mg every other day (qod)*	1 x 2.5 mg tablet
2.5 mg daily (qd)	1 x 2.5 mg tablet
5 mg daily (qd)	2x 2.5 mg tablet
10 mg (qd)	4x 2.5 mg tablet

Everolimus- for Dose Levels 4-6 and possible dose reductions	
Dose	Number of tablets & strength
25 mg (1/weekly) – 50% of dose level 4	2 x 10 mg tablet and 2 x 2.5mg tablet
30 mg (1/weekly) - 50% of dose level 5	3 x 10 mg tablet
35 mg (1/weekly) - 50% of dose level 6	3 x 10 mg tablet and 2 x 2.5mg tablet
40 mg (1/weekly) – 1 dose reduction from dose level 4	4 x 10 mg tablet
50 mg (1/weekly) – 1 dose reduction from dose level 5	5 x 10 mg tablet
60 mg (1/weekly) – 1 dose reduction from dose level 6	6 x 10 mg tablet
70 mg (1/weekly)	7 x 10 mg tablet

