Worst toxicity (CTCAE 4.03 Grade)*	Regimen Modifications for Ribociclib Management Recommendations	Regimen Modifications for Everolimus Management Recommendations
Stomatitis		
Grade 1 Minimal symptoms; normal diet	No dose adjustment required. Manage with non-alcoholic or salt water (0.9%) mouthwash several times per day	
Grade 2 Symptomatic but can eat and swallow modified diet	If everolimus is interrupted/discontinued, ribociclib should also be interrupted/discontinued. Resume ribociclib at same dose level if everolimus is resumed at same or lower dose level.	Interrupt everolimus until recovery to Grade ≤ 1. Reinitiate everolimus at same dose. If recurs at Grade 2, interrupt dose until recover to Grade ≤ 1. Resume at 50% of previous dose; change to every other day dosing if the reduced dose is lower than the lowest available strength. Manage with topical analgesic mouth treatments.
Grade 3 Symptomatic and unable to adequately eat or hydrate orally	If everolimus is interrupted/discontinued, ribociclib should also be interrupted/discontinued. Resume ribociclib at same dose level if everolimus is resumed at lower dose level.	Dose interruption of everolimus until recovery to Grade < 1. Resume at 50% of previous dose; change to every other day dosing if the reduced dose is lower than the lowest available strength.
Grade 4 Symptoms associated with life-threatening consequences	Discontinue ribociclib+everolimus	Discontinue everolimus and treat with appropriate medical therapy
Non-infectious pneumonitis		
Grade 1 Asymptomatic, radiographic findings only	No dose adjustment required. Initiate appropriate monitoring.	
Grade 2 Symptomatic but not interfering with Activities of Daily Living (ADL)	If everolimus is interrupted/discontinued, ribociclib should also be interrupted/discontinued. Resume ribociclib at same dose level if everolimus is resumed at same or lower dose.	Consider dose interruption of everolimus. Rule out infection and consider treatment with corticosteroids until symptoms improve to Grade < 1 Resume at 50% of previous dose; change to every other day dosing if the reduced dose is lower than the lowest available strength. Discontinue everolimus if failure to recover within 4 weeks.

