Grade 2	If everolimus is interrupted/discontinued, ribociclib should also be interrupted/discontinued. Resume ribociclib at same dose level if everolimus is resumed at same or lower dose.	If toxicity is tolerable, no dose adjustment required Initiate appropriate medical therapy and monitor. If toxicity becomes intolerable, interrupt dose until recovery to Grade ≤ 1. Re-initiate everolimus at same dose level. If the same toxicity recurs at grade 2, interrupt everolimus until recovery to grade ≤ 1 and re-initiate treatment at lower dose level (50% of previous dose).

Worst toxicity (CTCAE 4.03 Grade)*	Regimen Modifications for Ribociclib Management Recommendations	Regimen Modifications for Everolimus Management Recommendations
Grade 3	If everolimus is interrupted/discontinued, ribociclib should also be interrupted/discontinued. Resume ribociclib at same dose level if everolimus is resumed at lower dose.	Dose interruption until recovery to grade ≤ 1. Initiate appropriate medical therapy and monitor. Re-initiate everolimus at the next lower dose level (50% of previous dose). If toxicity recurs at grade 3, discontinue treatment study.
Grade 4	Discontinue ribociclib+everolimus	Discontinue everolimus and treat with appropriate medical therapy.

Severity Description: 1 = mild symptoms; 2 = moderate symptoms; 3 = severe symptoms; 4 = life-threatening symptoms

* Common Terminology Criteria for Adverse Events (CTCAE) version 4.03. All dose modifications should be based on the worst preceding toxicity.

** If Grade 3 or 4 hyperbilirubinemia is due to the indirect (non-conjugated) component only, and hemolysis as the etiology has been ruled out as per institutional guidelines (e.g., review of peripheral blood smear and haptoglobin determination), then continue treatment at the discretion of the Investigator.

***LFTs include albumin, ALT, AST, total bilirubin (fractionated if total bilirubin > 2.0 x ULN), alkaline phosphatase and GGT.

If dose reduction is required, the suggested dose is approximately 50% lower than the previously administered dose.

Ribociclib dose adjustment and management recommendation for ILD/pneumonitis (CTCAE v4.03)

Grade	Dose Adjustment and Management Recommendations
1 (asymptomatic)	No dose adjustment required. Initiate appropriate medical therapy and monitor as clinically indicated.
2 (symptomatic)	Interrupt ribociclib dose until recovery to Grade ≤1, then resume ribociclib at the next lower dose level*.

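### Table 11, other non-hematologic Grade 3: the everolimus restart rule equates one dose level down with 50%, but for weekly dosing Table 10 lists these as different doses

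*Combined protocol and SAP*

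**What the plan says.** **The cell at issue.** Table 11 (Section 6.2.3) gives restart rules for Phase 2. In the row for all other non-hematologic reactions, Grade 3, everolimus is interrupted until recovery to Grade 1 or lower. The cell then says "Re-initiate everolimus at the next lower dose level (50% of previous dose". The recurrent Grade 2 cell in the same block is worded more loosely: "re-initiate treatment at lower dose level (50% of previous dose".

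**Other everolimus reduction rules in Table 11.**
- Stomatitis (recurrent Grade 2, Grade 3), pneumonitis (Grades 2 and 3) and metabolic events (Grade 3): "Resume at 50% of previous dose; change to every other day dosing", with no mention of a dose level.
- Neutropenia Grade 4, febrile neutropenia Grade 3, and thrombocytopenia Grades 3 and 4: the next lower dose level, with no percentage.
- Footnote to the table: "If dose reduction is required, the suggested dose is approximately 50% lower than the previously administered dose".

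**Table 10 (Section 6.2.2)** is given as the source of the dose modification levels. Its weekly section has two lines per level. The 40 mg line is "1 dose reduction from dose level 4" and the 25 mg line is "50% of dose level 4". The 50 mg line is "1 dose reduction from dose level 5" and the 30 mg line is "50% of dose level 5". Level 6 has 60 mg and 35 mg in the same pattern.

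**Table 7 (Section 6.1.1)** gives the Phase 2 doses. Level 4 receives 50 mg weekly. Levels 5 and 6 also start at 50 mg weekly in Cycle 1 and may go to 60 mg from Cycle 2 at the investigator's discretion. No Phase 2 entry in Table 7 is 70 mg, although Section 2.3 anticipates escalation towards it.

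**The concern.** The cell gives two descriptions of one dose. They agree on the daily regimen, but on the weekly regimen each matches its own line of Table 10. A site that takes the level wording to Table 10 finds one dose; a site that takes the percentage finds a lower one. This is the restart dose after a Grade 3 toxicity, in the row that covers every non-hematologic reaction not listed separately, and the trial may run at up to three sites. What is at stake is the safety of the individual patient and consistent dosing between sites.

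The labels in Table 10 add a second difficulty. They refer to the assigned dose level, while the dose a Level 5 or 6 patient actually takes in Phase 2 starts at the Level 4 amount.

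**Working it through.** **Inputs.** Daily and weekly lines of Table 10 (Section 6.2.2); Phase 2 doses in Table 7 (Section 6.1.1); weekly dosing on Days 1, 8, 15 and 22, hence 4 doses per 28-day cycle (Table 7, note e).

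**Step 1. Does one level down equal 50% on the daily ladder?**

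| Current dose | Next lower line | Half of current dose |
|---|---|---|
| 10 mg | 5 mg | 5 mg |
| 5 mg | 2.5 mg | 2.5 mg |
| 2.5 mg | 2.5 mg every other day (1.25 mg/day) | 1.25 mg/day |

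Yes, at every step. The cell is consistent for daily everolimus.

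**Step 2. The same check on the weekly lines.** Percentage cut = 1 − new dose / current dose; ratio = one-level dose / 50% dose.

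| Current weekly dose | One reduction | 50% line | Ratio |
|---|---|---|---|
| 50 mg | 40 mg; 1 − 40/50 = 20.0% cut | 25 mg; 50.0% cut | 40/25 = 1.60 |
| 60 mg | 50 mg; 1 − 50/60 = 16.7% cut | 30 mg; 50.0% cut | 50/30 = 1.67 |
| 70 mg (only if given) | 60 mg; 1 − 60/70 = 14.3% cut | 35 mg; 50.0% cut | 60/35 = 1.71 |

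Per cycle, from 50 mg: 4 × 40 = 160 mg against 4 × 25 = 100 mg. From 60 mg: 4 × 50 = 200 mg against 4 × 30 = 120 mg. The two descriptions agree at no weekly dose.

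**Step 3. Which reading does the text favour?** The parenthesis in the cell says 50%. All five everolimus reduction cells for the named non-hematologic toxicities say 50% and nothing else. The footnote says about 50%, though only as a suggestion. The evidence points to 25 mg from 50 mg and 30 mg from 60 mg.

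**Step 4. Table 10 one-reduction lines read by assigned level, against the dose actually taken.**

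| Patient | Line for assigned level | Change from current dose |
|---|---|---|
| Level 5 on 50 mg | 50 mg | 50 − 50 = 0 mg |
| Level 6 on 50 mg | 60 mg | 60 − 50 = +10 mg |
| Level 6 on 60 mg | 60 mg | 60 − 60 = 0 mg |

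None of these lowers the dose.

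**The case against.** The strongest reply is that the cell settles its own question. The percentage follows directly in the same sentence, and 25, 30 and 35 mg are themselves lines of a table of dose modification levels. The Grade 3 stomatitis row supports this: its ribociclib cell describes everolimus as resumed at a lower dose level, while its everolimus cell sets that dose at 50%. The rules are also not rigid. Section 6.2.1 says only that reductions may be considered after Grade 3 toxicity, the Table 11 columns are headed as recommendations, and Section 6.2.1 requires variances to be discussed with the sponsor first unless action is urgent.

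Much of this stands. It makes the 1.60 to 1.67-fold difference a worst case that needs a site to act on the first half of the sentence and overlook the second. It does not remove the mismatch, because Table 10 labels a different weekly dose as one reduction. The sponsor-contact rule is weak protection here, since a site following either phrase may not think it is departing from the guideline.

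Three stronger readings are tempting and are not supported:
- **That the level wording is a stray phrase throughout Table 11.** The hematologic rows use it alone, so it is established usage there.
- **That Table 10 prescribes inadequate halvings for Levels 5 and 6**, for example 35 mg as half for a Level 6 patient on 50 mg (1 − 35/50 = a 30% cut). That needs a row label to override the rule, which refers to the previous dose. Half of 50 mg is 25 mg, and that line exists.
- **That the recurrent Grade 2 cell has the same conflict.** It says lower, not next lower, and 50% satisfies it.

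**Conclusion.** The point holds as a minor dosing-safety correction. For weekly everolimus, the Grade 3 catch-all cell equates two doses that Table 10 keeps apart: 40 and 25 mg from 50 mg, 50 and 30 mg from 60 mg. Most of the text favours 50%. A reader might infer that the intended dose is undetermined; that goes too far, although the sponsor should confirm the intent.

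The reach is small. Only weekly-dosed Phase 2 patients (Levels 4 to 6) who restart after such a toxicity are affected, and Section 9.7.1 expects at most 3 to 12 Phase 2 patients in all. The figures for 60 mg assume that the investigator has escalated; the 70 mg row applies only if that dose is given. No statistical analysis is affected.

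The labelling point holds in a limited form. The one-reduction lines for Levels 5 and 6 do not reduce the dose of a patient still on 50 mg. A careful clinician would notice, but a reduction table should not leave this to be noticed.

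**What to change.** 1. In the Grade 3 cell for other non-hematologic reactions, for weekly everolimus, delete the reference to the next lower dose level and state 50% of the dose the patient was receiving: 25 mg from 50 mg, 30 mg from 60 mg (and 35 mg from 70 mg, should that dose be given). The sponsor should confirm that this is the intent.
2. Relabel the six weekly reduction lines of Table 10 (25, 30, 35, 40, 50 and 60 mg) by current dose instead of assigned level, for example 25 mg as half of 50 mg and 40 mg as one step down from 50 mg. Keep the one-step lines, because the hematologic rows rely on them.
3. Optionally, align the recurrent Grade 2 cell in the same block.

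The footnote and the other rows of Table 11 can stay as they are. The cost is a wording amendment to one cell (two with the optional change) and six labels. All the doses are already in Table 10 with tablet counts, so no dose, visit, procedure or patient is added.

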6.2.3.1 Guidelines for the follow-up of laboratory hematologic abnormalities

In case of any occurrence of febrile neutropenia, neutropenia \geq grade 3, or thrombocytopenia \geq grade 3, hematology tests must be performed weekly (or more frequently if clinically indicated) until the event resolves to \leq grade 2. Subsequent monitoring must be performed every 3 weeks. (See Table 12)

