6.2.3 Follow-up for toxicities

An unscheduled visit should be performed in all cases below where toxicity monitoring is recommended more frequently than defined by the schedule of assessments.

Ongoing SAEs at the final safety evaluation visit or the end of study treatment visit (whichever is later) should be followed until they improve becoming non-serious events, stabilize, or return to baseline levels. Refer to [Section 8.2](#) for SAE.

Table 11 Criteria for post-tumor resection interruption and re-initiation of ribociclib+everolimus treatment

Worst toxicity (CTCAE 4.03 Grade)*	Regimen Modifications for Ribociclib Management Recommendations	Regimen Modifications for Everolimus Management Recommendations
HEMATOLOGICAL		
Anemia		
Grade 1 (Hemoglobin (Hgb) <LLN - 10.0 g/dL; <LLN - 6.2 mmol/L; <LLN - 100 g/L)	Continue regimen	Continue regimen
Grade 2 (Hgb <10.0 - 8.0 g/dL; <6.2 - 4.9 mmol/L; <100 - 80g/L)	Continue regimen	Continue regimen
Grade 3 (Hgb <8.0 g/dL; <4.9 mmol/L;	Dose interruption until recovery to grade ≤ 1. Re-initiate ribociclib at the same dose.	Dose interruption until recovery to grade ≤ 1. Re-initiate everolimus at the same dose.
Grade 4 (transfusion indicated Life-threatening)	Discontinue ribociclib	Discontinue everolimus
Neutropenia (ANC)		
Grade 1 (ANC < LLN - 1.5 x 10 ⁹ /L)	Continue regimen	Continue regimen
Grade 2 (ANC < 1.5 and ≥ 1.0 x 10 ⁹ /L)	Continue regimen	Continue regimen
Grade 3 (ANC < 1.0 and ≥ 0.5 x 10 ⁹ /L)	Dose interruption until recovery to ≥1.0x10 ⁹ /L (≤grade 2). Re-initiate ribociclib at the same dose level. If toxicity recurs at grade 3, temporary dose interruption until recovery to ≥1.0x10 ⁹ /L (≤grade 2). If resolved in ≤7 days, then maintain dose level. If resolved in >7 days, then reduce ribociclib dose to the next lower dose level.	Dose interruption until recovery to grade ≤2. Re-initiate everolimus at the same dose level. If ribociclib is interrupted/ discontinued, everolimus should also be interrupted/discontinued. Resume everolimus at same dose level if ribociclib is resumed at either the same or lower dose.
Grade 4 (ANC < 0.5 x 10 ⁹ /L)	Dose interruption until recovery to ≥1.0x10 ⁹ /L. Re-initiate ribociclib at the next lower dose level. If toxicity recurs at grade 4, discontinue ribociclib+everolimus	Dose interruption until recovery to grade ≤2. Re-initiate everolimus at the next lower dose level. If toxicity recurs at grade 4, discontinue ribociclib+everolimus

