Febrile neutropenia Grade 3 (ANC < 1.0 x 10 ⁹ /L, with a single temperature of ≥ 38.3 °C (101°F) or a sustained temperature of ≥ 38 °C (100.4°F) for more than one hour)	Dose interruption until improvement of ANC ≥1.0x10 ⁹ /L (≤Grade 2) and no fever. Restart at the next lower dose level. If febrile neutropenia recurs, discontinue ribociclib +everolimus.	Dose interruption until improvement of ANC ≥1.0x10 ⁹ /L (≤Grade 2) and no fever. Re-initiate everolimus at the next lower dose level. If febrile neutropenia recurs, discontinue ribociclib +everolimus.
Febrile neutropenia Grade 4 Life-threatening consequences; urgent intervention indicated	Discontinue treatment.	Discontinue treatment.

Worst toxicity (CTCAE 4.03 Grade)*	Regimen Modifications for Ribociclib Management Recommendations	Regimen Modifications for Everolimus Management Recommendations
Thrombocytopenia		
Grade 1 (PLT < LLN - $75 \times 10^9/L$)	Continue regimen	Continue regimen
Grade 2 (PLT < 75 and $\geq 50 \times 10^9/L$)	Dose interruption until recovery to grade ≤ 1 . Re-initiate ribociclib at the same dose.	Dose interruption until recovery to grade ≤ 1 . Re-initiate everolimus at the same dose.
Grade 3 (PLT < 50 and $\geq 25 \times 10^9/L$)	Dose interruption until recovery to grade ≤ 1 . Re-initiate ribociclib at the same dose level. If toxicity recurs at grade 3, temporary dose interruption until recovery to grade ≤ 1 and reduce ribociclib to the next lower dose level.	Dose interruption until recovery to grade ≤ 1 . Re-initiate everolimus at the next lower dose level. If toxicity recurs at grade 3, temporary dose interruption until recovery to grade ≤ 1 and reduce everolimus to the next lower dose level.
Grade 4 (PLT < $25 \times 10^9/L$)	Dose interruption until recovery to grade ≤ 1 . Re-initiate ribociclib at the next lower dose level. If toxicity recurs at grade 4: discontinue ribociclib	Dose interruption until recovery to grade ≤ 1 . Re-initiate everolimus at the next lower dose level. If toxicity recurs at grade 4: discontinue everolimus

Worst toxicity (CTCAE 4.03 Grade)*	Regimen Modifications for Ribociclib Management Recommendations	Regimen Modifications for Everolimus Management Recommendations
HEPATOTOXICITY (BILIRUBIN, SGPT/ALT, SGOT/AST)		
Total Bilirubin** without ALT/AST increase above baseline value (for patients with Gilbert Syndrome these dose modifications apply to changes in direct (conjugated) bilirubin only)		

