7.1 Protocol flow and visit schedule

[Table 13](#) lists all of the assessments and indicates when they are performed. Each post-surgical Phase 2 treatment cycle in patients is 28 days (the 28 days cycle length is fixed regardless of whether the dose of ribociclib+everolimus is withheld). All visits are to be scheduled according to the appropriate number of calendar days from Cycle 1 Day 1 of ribociclib+everolimus drug administration post-surgery. A visit window of ± 1 in Cycle 1 Days 8, 15, 22 and ± 3 days in Cycle 2 onward is allowed. PK sampling on Day 4/5 post-dose will have ± 5 min window for 0.5hr and 1 hour samples and ± 15 min window for remaining samples (2, 4, 7h).

Note: If treatment with ribociclib+everolimus is withheld at any time during the post-surgical phase (Phase 2), all study visits, and safety assessments should continue according to the appropriate number of calendar days from Cycle 1 Day 1 as per the schedule of assessments.

Surveillance imaging will adhere to current clinical standards, which include MR imaging at a minimum of every 3 months for Grade III/IV recurrent gliomas.

Table 13 Visit evaluation schedule

	PHASE 0						PHASE 2				Survival Follow Up Call/Letter
	Screening/ Baseline	Enrollment	At Home	Pre-surgical assess-ment	Craniotomy for resection tumor resection	Phase 0	Cycle 1	Cycle 2	Subsequent cycles	End of study treat-ment (EoT)	
Visit Number	1	2	n/a	3	4	5	6-9	10-13	14, 15,...	Last	
Day of cycle	-28 to-1	Day 1	Day 2 & 3	Day 4	Cohort 1&2 Day 5 or Cohort 3 Day 6	Post-Operative Visit	Day of Cycle	Day of Cycle	Day of Cycle	Last	30 days after last dose
Obtain Informed Consent	X										~every 3 months after safety phone call
Collect archival tissue	X										
Patient history											
Inclusion/exclusion criteria	X	Day 1 pre									
Diagnosis and extent of cancer	X										
Demography	X										
Relevant medical history/current medical conditions	X										
Prior antineoplastic therapy (meds, surgery, radiation)	X										
Prior/concomitant medications	X					Continuous				X	
Surgical and Medical Procedures	X	X		X	X	Continuous					
Phone Call / Letter											~Q3 months ¹³
Safety assessments											
MRI of brain	X ¹					X (post-op)	MR imaging minimum every 3 months			last MRI obtained	
Response Assessment (RANO)	X ¹					X (post-op)	minimum every 3 months			X	
Physical examination	X ²					X	1	1	1	X	
Performance status (ECOG)	X	X				X	1	1	1	X	
Height	X ²										
Weight	X ²					X	1	1	1	X	

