ECG (12-Lead)	X ²	X ^{2,4}		X ⁴	X ⁴	X	15 ⁵	1,15 ⁵	1 ^{5,6}	X	

Initial Version date: 10/16/2018

Revision date: 03/11/2019, 5/07/2019, 09/26/2019, 03/17/2020, 08/26/2024

	PHASE 0						PHASE 2					Survival Follow Up Call/Letter
	Screening/ Baseline	Enrollment	At Home	Pre- surgical assess- ment	Craniotomy for resection tumor resection	Phase 0 Follow - Up	Cycle 1 (28d)	Cycle 2 (28d)	Subsequent cycles (28d)	End of study treat- ment (EoT)	Safety Follow- up (phone)	
Visit Number	1	2	n/a	3	4	5	6-9	10-13	14, 15,...	Last		
Day of cycle	-28 to-1	Day 1	Day 2 & 3	Day 4	Cohort 1&2 Day 5 or Cohort 3 Day 6	Post- Operative Visit	Day of Cycle	Day of Cycle	Day of Cycle	Last	30 days after last dose	~every 3 months after safety phone call
Vital signs	X ²					X	1, 15	1, 15	1	X		
Adverse events			Continuous		first study drug administration up to 30 days after last dose of study treatment					X		
Laboratory assessments												
Hematology (CBC w/Diff)		X		X ⁷		X	15	1, 15	1	X		
Chemistry (CMP, Mg+, Phos)		X ²		X ⁷		X	15	1, 15	1	X		
eGFR ³		X ²		X ⁷								
Coagulation (PT/INR, PTT)		X ²		X ⁷								
Lipid panel		X ²								1 ⁸		
Urinalysis (dipstick) with microscopic analysis		X ²					15	1	1			
Pregnancy test (serum HCG) if applicable		X ²										
Pregnancy test (urine) if applicable						X	1	1	1	X		
Study Drug												
Drug administration		X ⁹	X ⁹	X ⁹	X ⁹		Daily Days 1-28 day cycle ¹⁰					
Review of Home Dosing Diary and Symptom Diary				X			1	1	1	X		
PK & Biomarker sample collections												
PK Blood Sampling		X		X ¹¹	X ¹¹		1, 8, 15, 22 10	1, 8, 15, 22 10				
Collection of PK CSF					X							
Collection of PK/PD Tumor tissue					X					X ¹²		
Biomarker blood collection		X ²										

1 | The most recent MRI scan available should be utilized.

	PHASE 0						PHASE 2					Survival Follow Up Call/Letter
	Screening/ Baseline	Enrollment	At Home	Pre-surgical assessment	Craniotomy for resection tumor resection	Phase 0	Cycle 1	Cycle 2	Subsequent cycles	End of study treatment (EoT)	Safety Follow-up (phone)	
Visit Number	1	2	n/a	3	4	5	6-9	10-13	14, 15,...	Last		
Day of cycle	-28 to-1	Day 1	Day 2 & 3	Day 4	Cohort 1&2 Day 5 or Cohort 3 Day 6	Post-Operative Visit	Day of Cycle	Day of Cycle	Day of Cycle	Last	30 days after last dose	~every 3 months after safety phone call

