2	Screening assessment may be completed at Day 1 predose, if completed at screening, does not need to be repeated at Day 1 pre-dose except for ECG and ECOG. Results must be available to confirm eligibility prior to dosing.											
3	Estimated glomerular filtration rate (eGFR)											
4	ECG Day 1 Pre-dose, Day 1: 2-4 hrs post-dose, and pre-surgical assessment (can be completed on Day 4 or Day 5 (Cohort 1&2) / Day 6 (Cohort 3)).											
5	ECG Pre-dose and 2-4 hours post dose on C1D15, C2D15, C3D1, C6D1; C9D1; and every 3 rd cycle...											
6	ECG Pre-dose C2D1, C4D1, C5D1; C7D1, C8D1, C10D1, C11D1; and every 1st and 2nd cycle...											
7	Performed at pre-surgical assessment as per SOC on Day 4 (can be completed on Day 5 (Cohort 1&2) or Day 6 (Cohort 3)).											
8	Lipid panel performed every 4th cycle D1											
9	Study drugs are administered in the clinics on D1, D4 and D5. Patients may take medications at home on D2 and D3											
10	Trough blood sample is collected prior to the drug administration on that day. Study drugs are administered in the clinics on the clinic visit days 1, 8, 15, 22.											
11	Blood samples will be obtained on Day 4 (the day before the surgery for Cohorts 1 & 2; 2 days before surgery for Cohort 3) at pre-dosing (trough level), 0.5, 1, 2, 4, 7 hours post dose (\pm 5 min window for 0.5hr and 1hr; \pm 15min window for 2, 4, 7hr samples). A pre-dosing (trough level) blood sample will also be obtained on Day 5 and a sample will be collected intra-operatively. In Dose Level 4+ only, PK blood sampling will occur at the same timepoints (pre, 0.5, 1, 2, 4, 6, 8 and 24) but will be obtained on Day 5 (the day of surgery); the 24 hour sample will be obtained on Day 6.											
12	Only Patients that have a recurrence and undergo an additional surgery for tumor resection											
13	The start of follow up for long-term survival begins following completion of the Day 30 safety follow up call. Subjects will continue to be followed until death or withdrawal of consent for the collection and reporting of data or lost to follow-up for up to 5 years. Public records may be used to collect survival data, i.e., obituary notices and public database searches for survival information.											

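### Weekly platelet counts start at Grade 3 and stop at Grade 2, but Table 11 holds both drugs from Grade 2 until Grade 1 or lower

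*Combined protocol and SAP*

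**What the plan says.** **When treatment is held.** In Table 11 (Section 6.2.3), thrombocytopenia of Grade 2, 3 or 4 interrupts both drugs until Grade 1 or lower. The restart dose depends on the grade:

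- Grade 2: both drugs at the same dose; for everolimus, "Re-initiate everolimus at the same dose".
- First Grade 3: ribociclib at the same level, everolimus one level lower.
- Repeat Grade 3: "If toxicity recurs at grade 3, temporary dose interruption until recovery to grade" 1 or lower again, with both drugs reduced.
- First Grade 4: both drugs one level lower.

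**When counts are required.** Section 6.2.3.1 covers febrile neutropenia, and neutropenia or thrombocytopenia of Grade 3 or higher. For these, "hematology tests must be performed weekly (or more frequently if clinically indicated) until the event resolves to" Grade 2 or lower. After that, "Subsequent monitoring must be performed every 3 weeks". Table 12 repeats the rule.

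**Routine schedule.** Table 13 lists hematology in Phase 2 on Cycle 1 Day 15, Cycle 2 Days 1 and 15, and then Day 1 of each 28-day cycle. A hold does not change this. Section 7.1 says that when treatment is withheld "all study visits, and safety assessments should continue according to the appropriate number of calendar days from Cycle 1 Day 1". Section 6.2.3 adds: "An unscheduled visit should be performed in all cases below where toxicity monitoring is recommended more frequently than defined by the schedule of assessments".

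**The concern.** One rule serves neutrophils and platelets, but the two have different restart grades. For platelets, the required frequency falls from weekly to every 3 weeks while both drugs are still held and before the restart grade is reached. A first Grade 2 platelet event also stops both drugs, yet sets off no added count, so the unscheduled-visit provision has nothing to act on.

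Two things are at stake:

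- **Hold length.** Recovery to Grade 1 can go unseen until the next required count, so the length of a hold depends on whether a site tests beyond the minimum.
- **Restart dose.** Section 6.2.1 bases dose changes on the worst preceding grade. An unseen fall from Grade 2 to Grade 3 or 4 would change the correct restart dose.

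Section 6.1.5 promises special attention to blood counts, and Section 1.2.2.3 lists cytopenia and hemorrhage among the class effects of mTOR inhibitors.

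**Working it through.** The plan gives no figure to reproduce. The check compares thresholds and then counts days.

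**Thresholds side by side**

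| Event | Hold ends (Table 11) | Weekly counts start (6.2.3.1, Table 12) | Weekly counts end | Match? |
|---|---|---|---|---|
| Neutropenia, Grade 3-4 | Grade 2 or lower | Grade 3 | Grade 2 or lower | Yes |
| Thrombocytopenia, Grade 3-4 | Grade 1 or lower | Grade 3 | Grade 2 or lower | No: ends one grade early |
| Thrombocytopenia, first onset at Grade 2 | Grade 1 or lower | Not triggered | Not applicable | No |

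**Longest required interval from Cycle 3.** Inputs: hematology on Day 1 of each fixed 28-day cycle (Table 13, Section 7.1) and the 3-week rule (Section 6.2.3.1). Days are nominal, before the visit window of plus or minus 3 days. I assume the 3 weeks run from the count that first shows Grade 2.

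*Grade 3-4 event that reaches Grade 2 on cycle Day d.* The next required count is on Day min(d + 21, 29), where Day 29 is Day 1 of the next cycle.

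- d = 1: min(22, 29) = 22, a gap of 21 days
- d = 8: min(29, 29) = 29, a gap of 21 days
- d = 15: min(36, 29) = 29, a gap of 14 days
- d = 22: min(43, 29) = 29, a gap of 7 days

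*First Grade 2 event found at the Day 1 visit.* No added rule applies, so the next required count is on Day 29: 29 - 1 = 28 days.

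**Illustration for Dose Level 4 and above.** Everolimus is due on Days 1, 8, 15 and 22 (Table 7, note e). Suppose a count on Day 1 shows Grade 2 after a Grade 3 event, and platelets are back at Grade 1 by Day 8. Weekly testing allows a restart on Day 8. The required minimum allows it on Day 22, so the Day 8 and Day 15 doses are lost.

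**Cycles 1 and 2.** The listed counts from Cycle 1 Day 15 are 14 days apart (Cycle 1 Day 15, Cycle 2 Day 1, Cycle 2 Day 15, Cycle 3 Day 1). Patients also attend on Days 1, 8, 15 and 22 for trough samples (Section 4.1.2). The 21- and 28-day figures therefore apply only from Cycle 3.

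**The case against.** The strongest reply is that no rule is contradicted. A hold until Grade 1 or lower cannot be ended without a count, so Table 11 itself implies testing. Section 6.2.3.1 allows more frequent tests. Section 7.2.2 lets the investigator evaluate safety at any time. Sections 6.2.1, 8.1.1 and 8.1.2.1 require follow-up of interruptions, adverse events and abnormal laboratory values. This stands: the intervals are minimums on paper, not a forecast of practice, and a reader who infers that platelets go unmonitored during a hold goes too far. But none of these duties sets an interval beyond the scheduled visits, and the one dated rule relaxes too early for platelets.

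It also stands that the consequence is small. Both drugs are already stopped, so missing a worse grade needs a further fall and recovery between two counts. Section 9.7.1 expects at most 3 to 12 Phase 2 patients.

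Several wider readings are tempting but not supported:

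- **Anemia and dyslipidemia.** Grade 3 of either also holds both drugs and neither is in Table 12. But that table says it covers selected toxicities only, so leaving them out is a choice, not a threshold that fails to fit. Section 7.1 has "Lipid panel performed every 4th cycle D1", which is 4 x 28 = 112 days. Calling that the monitoring gap overlooks the instruction to monitor in the same Table 11 cell that imposes the hold.
- **A uniform liver precedent.** Weekly liver tests for bilirubin do run to its restart grade. ALT and AST holds run to baseline in Table 11, while weekly tests end at Grade 1 or lower (Section 6.2.3.2). The protocol does not always tie the two together.
- **Restart below Grade 1.** Table 11 prints a strict less-than sign for some Grade 3 events. This is probably a lost underline in the text extraction and supports no point.

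**Conclusion.** The platelet mismatch holds on the current text. Weekly counts start one grade later than the hold (Grade 3 against Grade 2) and stop one grade before it ends (Grade 2 against Grade 1). From Cycle 3 this permits up to 21 days between required counts after a Grade 3-4 event has reached Grade 2, and up to 28 days for a first Grade 2 event.

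The figures rest on nominal visit days, on the 3-week rule running from the first Grade 2 count, and on sites testing no more than required. The documents give no frequency of platelet holds, so the number of patients affected cannot be stated.

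A reader might infer that dose finding is compromised. It is not: Section 6.1.3 limits the DLT window to the first 5 days of Phase 0 or the first 28-day cycle of Phase 2, before the intervals described here arise. DLT, MTD, RP2D and every statistical figure are unchanged. The point is a cheap improvement to safety monitoring, of low severity.

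**What to change.** In Section 6.2.3.1 and Table 12, give thrombocytopenia its own line: weekly hematology for any thrombocytopenia that interrupts treatment (Grade 2 or higher), until the Table 11 restart grade (Grade 1 or lower). Leave the neutropenia rule unchanged. The longest required interval during a platelet hold then becomes 7 days.

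Cost per 28-day hold starting on Day 1, from Cycle 3:

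- First Grade 2 event: counts on Days 8, 15 and 22, so 3 extra.
- Grade 3-4 event already at Grade 2: counts on Days 8 and 15, so 2 extra, because Day 22 is already required.

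These use the unscheduled visits that Section 6.2.3 already provides for. In Cycles 1 and 2 the added counts fall on the weekly trough-sample visits.
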